---

**DOCUMENT VERSION HISTORY**

Date	Version	Reason for Revision
12/05/2021	1.0	Initial
18/10/2021	2.0	Correction of typos and inconsistencies. Inclusion of requirements received from RAs and ECs and incorporated in country specific versions: 1.1 BEL, 1.1 FRA, 1.2 FRA, 1.1 GBR, 1.1 IRL
30/08/2022	3.0	Update of study endpoints and statistical analysis section. Administrative updates.
24/05/2023	4.0	Non-Substantial Amendment Sub group analysis wording in statistical section (no change in primary or secondary endpoints), clarification if patients can not attend study visits or key safety assessments, clarification on IMP delivery. Minor administrative updates

## ABBREVIATIONS

3-NT	3-Nitrotyrosine
4HNE	4-hydroxy-2-nonenal
8-OHdG	8-hydroxyguanosine
ADR	Adverse Drug Reaction
AE	Adverse Event
AESI	Adverse Event of Special Interest
AIS	Acute Ischaemic Stroke
ALS	Amyotrophic Lateral Sclerosis
ALSFRS-R	ALS Functional Rating Score – revised
ALSAQ-40	ALS Assessment questionnaire 40
ALT	Alanine transaminase
aPTT	Activated partial thromboplastin time
AST	Aspartate transaminase
AUC	Area Under the Curve
BID	Twice Daily
BUN	Blood urea nitrogen
CAFS	Combined Assessment of Function and Survival
CAS	Chemical Abstracts Service
CHMP	Committee for Human Medicinal Products
CI	Confidence Interval
CK	Creatinine kinase
C max	Maximum concentration
CNS	Central Nervous System
CSF	Cerebrospinal Fluid
CYP	Cytochrome P450
CV	Coefficient of Variation
DSMB	Data Safety Monitoring Board
EC	European Committee
ECAS	Edinburgh Cognitive and behavioural ALS Screen
eGFR	Estimated glomerular filtration rate
EMA	European Medicines Agency
EMG	Electromyography
fALS	familial Amyotrophic Lateral Sclerosis
FDA	Food and Drug Administration
FTD	Frontotemporal dementia
FVC	Forced Vital Capacity
G93A	G93A-human Cu/Zn superoxide dismutase

---

GGT	Gamma-glutamyl transpeptidase
GI	Gastrointestinal
hct	Haematocrit
HEK	Human Embryonic Kidney
hERG	human Ether-a-go-go-Related Gene
hgb	Haemoglobin
hOAT	Human Organic Anion Transporter
HSP	Hereditary Spastic Paraparesis
IC 50	Half Maximal Inhibitory Concentration
IDMC	Independent Data Monitoring Committee
IE	Intercurrent Event
INN	International Non-proprietary Name
iNOS	Inducible Nitric Oxide Synthase
IV	Intravenous
IUPAC	International Union of Pure and Applied Chemistry
Km	Michaelis constant
LD 50	Median Lethal Dose
LDH	Lactate dehydrogenase
LMN	Lower Motor Neurons
MMRM	Mixed Model for Repeat Measures
MND	Motor Neuron Disease
MoA	Mechanism of Action
MOS	Margin of Safety
mSOD1	Mutated Superoxide Dismutase 1
MVV	Maximum Voluntary Ventilation
NAA	N-Acetyl Aspartate
NCS	Nerve Conduction Study
NF	National Formula
NFL	Neurofilament Light
NIPPV	Non-invasive Positive Pressure Ventilation
NMR	Nuclear Magnetic Resonance spectroscopy
NOAEL	No Observed Adverse Effect Level
Nrf2	Nuclear erythroid 2-related factor 2
OAT	Organic Anion Transporter
OD	Once Daily
P75 ECD	Extracellular domain of neurotrophin receptor p75
PAP	Pharmacokinetics Analysis Plan
PEG	Percutaneous Endoscopic Gastrostomy
PEG 400	Polyethylene glycol 400
PK	Pharmacokinetic(s)
PLP	Pyridoxal Phosphate
PLS	Primary Lateral Sclerosis

---

PMM	Pattern Mixture Modeling
PNS	Peripheral Nerve System
POC	Proof of concept
PTT	Prothrombin Time
Q1, Q3	First quarter, third quarter
QoL	Quality of Life
RBC	Red blood cell
RDW	Red cell distribution width
RNA	Ribonucleic acid
ROS	Reactive Oxygen Species
SAE	Serious Adverse Event
sALS	Sporadic Amyotrophic Lateral Sclerosis
SAH	Subarachnoid Haemorrhage
SAP	Statistical Analysis Plan
SD	Standard Deviation
SLS	Sodium Laurilsulfate
SOC	Standard of Care
SOD1	Superoxidase Dismutase 1
SULT	SulfoTransferase
SVC	Slow Vital Capacity
$t_{1/2}$	Half-life
TDP-43	Transactive response DNA/RNA Binding Protein 43
TEAE	Treatment Emergent Adverse Event
TID	Three Times Daily
$t_{max}$	Time to peak concentration
TW	Treeway
UGT	UDP-glucuronosyltransferases
UMN	Upper Motor Neurons
US	United States of America
WBC	White blood cell
WFN	World Federation of Neurology
WHO	World Health Organisation

## 1. SYNOPSIS

TITLE:	A multicenter, randomized, double-blind, placebo-controlled study to investigate the efficacy and safety of FAB122 in patients with Amyotrophic Lateral Sclerosis
THE SPONSOR STUDY CODE:	FAB122-CT-2001
EudraCT NUMBER:	2020-003376-40
SPONSOR:	Ferrer Internacional, S.A. Barcelona, Spain
STUDY PHASE:	PHASE III
STUDY DESIGN:	
Multicenter, multinational, double-blind, randomized (2:1), placebo-controlled Phase III study to investigate the efficacy and safety of 100 mg FAB122 (former TW001) once daily as oral formulation in ALS patients.
 
Subjects will be screened to assess whether they comply with all enrolment criteria. Approximately 300 patients will be randomized to 100 mg FAB122 or matched placebo in a 2:1 ratio. Patients will be stratified by;
 
1)their ALS progression rate at the start of the study (the slope ALSFRS-R score from time of first symptoms till Screening <1.0 vs. ≥1.0), 2)additional co-medication for ALS (a. riluzole, b. no riluzole).
 
Riluzole (100 mg/day or less) may be used as background (add-on) therapy. Patients on riluzole should be on stable doses at the start of the trial and for at least 30 days before the initiation of the study drug. It will not be allowed to initiate riluzole therapy during the trial. Additional supportive Standard Of Care (SOC) treatments will be allowed in all patients and will be standardized as much as possible.
 
Subjects will receive double-blind treatment up to a maximum of 72 weeks. The study is planned to continue until the last randomized subject has reached 48 weeks of follow-up (or has reached an intercurrent event) AND the first one third of the subjects randomized (100) have reached 72 weeks of follow up (or has reached an intercurrent event). Subjects who discontinue treatment before week 72 will be followed as much as possible according to the planned visit schedule.
 
Subjects will visit the clinic at Screening, Baseline, Week 4, Week 12, and every 12 weeks thereafter. Monthly telephone visits are performed in between the visits to the clinic until Week 48.
 
Blood sampling for FAB122 plasma concentrations will be done in ~90 subjects treated with the study drug.
 
After a subject completed the study (max at 72 weeks), he/she will be offered

	the possibility to roll over in an open label extension trial in which all subjects will be offered to receive FAB122.
STUDY PARTICIPANTS:	
Study Population	ALS patients
Inclusion Criteria	
In order to be eligible for participation in this trial, a subject must meet all of the following criteria:
 
 
1. Age 18 – 80 years (both inclusive), male or female;
 
2. Diagnosis of definite, probable, probable laboratory supported or possible ALS as based on the El Escorial and the revised Airlie House diagnostic criteria for ALS;
 
3. Onset of first symptoms* no longer than 24 months prior to randomization;
 
 
*Date of onset is the date the patient reported one or more of the following symptoms:
 
 
▪ Muscle weakness in limbs
 
▪ Speech/swallowing difficulties
 
▪ Respiratory symptoms: dyspnea was noticed
 
 
 
4. SVC equal to or more than 70% of the predicted normal value for gender, height and age at screening visit;
 
5. Change in ALSFRS-R score between 0.35 points and 1.5 points per month (both inclusive) in the period from onset of first symptoms to the Screening visit;
 
6. Patients on riluzole should be on stable doses <math>\geq</math>30 days prior to the baseline visit and this dose should be maintained during the entire trial.
 
7. A female subject should not be able to become pregnant and needs to meet at least one of the following criteria: 
 
• female subject who is not of reproductive potential is eligible without requiring the use of contraception. A woman is considered not having childbearing potential when becoming post-menopausal unless permanently sterile. Permanent sterilisation methods include hysterectomy, bilateral salpingectomy and bilateral oophorectomy. A postmenopausal state is defined as no menses for 12 months without an alternative medical cause.
 
• female who is of reproductive potential and has a negative pregnancy test at screening and at baseline and is non-lactating. A female subject who is of reproductive potential agrees to use (or have their partner use) or practicing adequate birth control methods starting from the time of consent through 30 days after the last dose of study therapy. Longer periods of birth control may be required per local requirements. Acceptable methods of birth control include combined (estrogen and progestogen containing) hormonal contraception associated with inhibition of ovulation (oral, intravaginal, transdermal), progestogen-only hormonal contraception associated with inhibition of ovulation
 
 
 


	
(oral, injectable, implantable), intrauterine device in place for <math>\geq 3</math> months, intrauterine hormone-releasing system, bilateral tubal occlusion or vasectomised partner.
 
8. A male patient must:
 
 
• agree he will not donate sperm during the study and until 104 days after the last dose, AND
 
• use a condom during sexual intercourse with pregnant or non-pregnant women of childbearing potential (WOCBP) partner even if he is vasectomized
 
• in addition WOCBP partner of the male patient must use the following acceptable methods of birth control during the study and until 104 days after the last dose: combined (estrogen and progestogen containing) hormonal contraception associated with inhibition of ovulation (oral, intravaginal, transdermal), progestogen-only hormonal contraception associated with inhibition of ovulation (oral, injectable, implantable intrauterine device in place for <math>\geq 3</math> months, intrauterine hormone-releasing system, bilateral tubal occlusion or vasectomised partners);
 
 
9. Capable of providing informed consent and complying with trial procedures.

Exclusion Criteria	
A subject must not meet one or more of the following criteria:
 
 
1. Diagnosis of Primary Lateral Sclerosis;
 
2. Diagnosis of Frontotemporal Dementia;
 
3. Diagnosis of other neurodegenerative diseases (e.g. Parkinson disease, Alzheimer disease);
 
4. Diagnosis of polyneuropathy;
 
5. Other causes of neuromuscular weakness;
 
6. Have a significant pulmonary disorder not attributed to ALS and/or require treatment interfering with the evaluation of ALS on respiratory function;
 
7. Use of intravenous (IV) edaravone within 6 months of the screening visit;
 
8. Use of mechanical ventilation (invasive or non-invasive) at Screening;
 
9. Renal impairment as indicated by a creatinine clearance of less than 50 mL/min;
 
10. Subject has a history of clinically significant hepatic disease, hepatitis or biliary tract disease, ALT/AST levels <math>\geq 3 \times \text{ULN}</math>, bilirubin levels <math>\geq 2 \times \text{ULN}</math> or subject has a positive screening test for HIV, hepatitis B or C;
 
11. Presence of any of the following clinical conditions: 
 
a. Unstable cardiac, pulmonary, endocrine, hematologic or active infectious disease
 
b. Severe active psychiatric illness e.g. psychosis, untreated major depression within 90 days of the screening visitSignificant cognitive impairment,
 
 
 

	
clinical dementia or psychiatric illness
 
c. Cancer that is currently under active treatment or is likely to require treatment during the trial that may alter the subject's function and interfere with assessment of ALS disease progression.
 
12. Any comorbidity that may interfere with the functions as scored with the ALSFRS-R;
 
13. History of known sensitivity or intolerance to edaravone, to any related compound, or to any of the excipients;
 
14. Exposure to any investigational drug within 30 days of the screening visit or 5 half-lives, whichever is longer;
 
15. Current substance or alcohol dependence.
 
16. For patients undergoing optional CSF sampling: any condition that according to the investigator criteria is contraindicated for the procedure (e.g. space-occupying lesion with mass effect, increase of intracranial pressure due to increased CSF pressure; posterior fossa mass; Arnold-Chiari malformation; anticoagulant medication; coagulopathy; uncorrected bleeding diathesis; congenital spine abnormality; and skin infection at puncture site

SAMPLE SIZE:	Total of 300 ALS patients, randomized 2:1 to FAB122 100 mg and placebo, respectively
PLANNED STUDY PERIOD:	
2 Years
 
Double-blind treatment is planned to continue until the last randomized subject has reached 48 weeks of follow-up (or has reached an intercurrent event (IE)) AND the first one third of the subjects randomized (100) have reached 72 weeks of follow-up (or has reached an intercurrent event). The maximum treatment duration for a subject in this study is 72 weeks.

PLANNED RECRUITMENT PERIOD:	10 Months
STUDY SITES	Approximately 30 sites
OBJECTIVES AND OUTCOME MEASURES:	
PRIMARY OBJECTIVE:	To assess the effect of treatment with 100 mg of FAB122 on disease progression in patients with ALS
SECONDARY OBJECTIVES:	
 
1. To evaluate the effect of treatment with FAB122 on survival
 
2. To evaluate the safety and tolerability of FAB122
 
3. To evaluate the effect of treatment with FAB122 on quality of life (QoL)
 
4. To evaluate the effect of treatment with FAB122 on cognitive functioning
 
5. To evaluate the pharmacokinetics (PK) of FAB122
 

EXPLORATORY OBJECTIVES	
 
1. To evaluate the PK interaction of FAB122 and riluzole
 
2. To explore and identify biomarkers that inform the scientific understanding of ALS and/or their therapeutic treatments
 

PRIMARY ENDPOINT:	Change from baseline in Amyotrophic Lateral Sclerosis Functional Rating Scale – Revised (ALSFRS-R) score after 48 weeks
SECONDARY ENDPOINTS:	
Key secondary endpoints
 
 
1. Combined assessment of function and survival (CAFS) at 48 and 72* weeks;
 
2. Survival time, i.e. time to death, tracheostomy or initiation of non-invasive ventilation for more than 20 hours a day for more than 10 consecutive days, over 72 weeks.
 
 
Efficacy
 
 
1. Change from baseline in ALSFRS-R score after 24 and 72* weeks;
 
2. The slope of the decrease in ALSFRS-R score over time at 24, 48 and 72* weeks;
 
3. Change from baseline in ALSFRS-R score on Bulbar function (question 1-3 of the ALSFRS-R) after 24, 48 and 72* weeks;
 
4. Change from baseline in ALSFRS-R score on Fine motor function (question 4-6 of the ALSFRS-R) after 24, 48 and 72* weeks;
 
5. Change from baseline in ALSFRS-R score on Gross motor function (question 7-9 of the ALSFRS-R) after 24, 48 and 72* weeks;
 
6. Change from baseline in ALSFRS-R score on Respiratory function (question 10-12 of the ALSFRS-R) after 24, 48 and 72* weeks;
 
7. Time to a 3, 6, 9 and 12 points change or death from baseline in ALSFRS-R score, over 72* weeks;
 
8. Proportion of subjects with change from baseline in ALSFRS-R score at 24, 48 and 72* weeks in categories: categories will include change <math>\geq 0</math>, change between <math><0</math> and <math>\geq -1</math>, change between <math><-1</math> and <math>\geq -2</math> etc.;
 
9. Time to change in clinical staging or death (King's staging system and MiToS) over 72* weeks;
 
10. Overall survival: Proportion of subjects alive (survival rate) after 24, 48 and 72* weeks;
 
11. Proportion of subjects alive and no tracheostomy, or no initiation of non-invasive ventilation for more than 20 hours a day for more than 10 consecutive days after 24, 48 and 72* weeks;
 
12. Change from baseline in slow vital capacity (SVC, liters) at 24, 48 and 72* weeks;
 
13. Change from baseline in the overall mega score for the hand-held dynamometer (HHD) at 24, 48 and 72 weeks.
 
 
QoL
 
 
1. Change from baseline in the total score on the ALS Assessment Questionnaire-40-Item (ALSAQ-40) Form at 24, 48 and 72* weeks;
 

	
2. Change from baseline in EuroQoL – 5 Dimensions-5 Levels (EQ-5D-5L) questionnaire score and health related QoL at 24, 48 and 72* weeks.
 
3. Change from baseline in Visual Analogue Scale (VAS) score at 24, 48 and 72* weeks.
 
Cognition
 
 
1. Proportion of subjects with a change of <math>\geq 8</math>, <math>\geq 4</math>, and <math>\geq 9</math> for ALS Specific, ALS Non-Specific, and ECAS (Edinburgh Cognitive and behavioural ALS Screen) total score;
 
2. Change from baseline for ALS Specific, ALS Non-Specific, and ECAS total score at 24, 48 and 72* weeks;
 
3. Time to a mean change of <math>\geq 8</math>, <math>\geq 4</math>, and <math>\geq 9</math> for ALS Specific, ALS Non-Specific, and ECAS total score.
 
 
Pharmacokinetics
 
(Population) PK parameters of FAB122 and riluzole
 
*All secondary endpoints at 72 weeks will be analyzed for the subgroup of patients that reach 72 weeks (or IE).

EXPLORATORY ENDPOINTS:	
Pharmacokinetics
 
PK interaction between FAB122 and riluzole
 
Biomarkers
 
 
1. Change from baseline in the prognostic ALS biomarker neurofilament light (NFL)
 
2. Change from baseline in the ALS biomarkers creatinine and creatinine kinase
 
3. Change from baseline in the ALS biomarker Urinary extracellular domain of neurotrophin receptor p75 (Urinary P75ECD)
 
4. Change from baseline of oxidative stress biomarker 8-hydroxyguanosine (8-OHdG)
 
 
Health economics
 
Cost-Utility analysis of treatment with FAB122

SAFETY ENDPOINTS	
 
1. Nature, frequency and severity of Treatment Emergent Adverse Events;
 
2. Parameters derived from vital signs and 12-lead electrocardiogram (ECG);
 
3. Parameters derived from laboratory tests (hematology, biochemistry, urinalysis);
 
4. Proportion of patients that drop out due to adverse events.
 

INTERVENTION(S):	
IMP(S):	FAB122:  Fasted daily dose of 100 mg FAB122 granules for oral solution in single sachets, which has to be dissolved in 100 mL water prior to administration, or matched placebo in a 2:1 ratio, respectively.
nIMP(S):	Riluzole:  The use of riluzole is allowed as add-on therapy on top of other supportive SOC treatments (such as symptomatic treatment of muscle spasms, pain, insomnia, dysphagia and emotional instability) during the study. Subjects taking riluzole must be on stable dosage $\geq 30$ days prior to the baseline visit. The riluzole dose must not exceed the recommended dose of 100 mg/day.  Riluzole will not be provided for the participating sites.
COMPARATOR:	Placebo
STATISTICAL METHODS:	The sample size estimation is based on the primary endpoint: the change from baseline in ALSFRS-R score after 48 weeks of follow up. A difference of 3.0 points between FAB122 treatment arm and placebo is assumed with a (pooled) standard deviation of 7.5 and an allocation ratio of 2:1 (FAB122: Placebo). With these assumptions, a total sample size of 300 (200 patients on FAB122 and 100 on placebo) is needed to achieve 90% power to detect the difference of 3.0 points between the two treatment groups at a 5% (2-sided) level of significance.  The primary analysis will be performed on the modified intent-to-treat population (mITTs), i.e. all randomized patients who had at least one treatment intake. The analysis of the primary endpoint will be also assessed with the PP and ITT populations as per sensitivity analysis.

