### 11.2. Sample Size Determination

The sample size estimation is based on the primary endpoint: the change from baseline in ALSFRS-R score after 48 weeks. A difference of 3.0 points between FAB122 treatment arm and placebo is assumed with a (pooled) standard deviation of 7.5 and an allocation ratio of 2:1 (FAB122:Placebo). With these assumptions, a total sample size of 300 (200 patients on FAB122 and 100 on placebo) is needed to achieve 90% power to detect the difference of 3.0 points between the two treatment groups at a 5% (2-sided) level of significance.

The standard deviation of 7.5 is based on recent study results with edaravone using a similar trial population as applied in this trial, where standard deviations varied between 3.4 and 6.9 (The Writing Group on behalf of the Edaravone (MCI-186) ALS 19 Study Group. 2017 b, 2017;). The variability in this study can be expected to be somewhat higher due to the change of formulation and due to the fact that in this study patient can use riluzole as background therapy.

The hypothesis in this study includes detection of a difference of 3 points in ALSFRS-R at week 48 between the two treatment arms. The patients in the placebo group in ALS studies typically deteriorate by 1 point per month, so 12 points in 12 months. A difference of 3 points therefore corresponds to a 25% difference in deterioration, which is considered clinically significant.

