## 5.2 Missing or excluded data or intercurrent events

### *Efficacy data – intercurrent events*

The intercurrent events during the study can be broadly classified as terminal and non-terminal intercurrent events. Death or “real” loss to follow-up are considered terminal intercurrent events, wherein there is absolutely no data available for these patients after the occurrence of the event. The other intercurrent events are non-terminal, where there is a possibility of collecting data from these patients after the occurrence of the intercurrent event (ICE).

Note that per design of the study, only 100 patients will be followed until week 72. The non-available data for the ~200 patients between week 48 and 72 will not be considered as ICE.

Regarding intercurrent events, following ICH E9 (R1), two types of strategies will be applied for the primary statistical analysis performed for the primary endpoint and utilizing the primary analysis population (mITT).

The “Treatment Policy” strategy will be applied to the following intercurrent events:

- Treatment discontinuation due to adverse events.
- Treatment discontinuation due to lack of efficacy.
- Other unforeseen treatment related reasons (i.e. due to efficacy or safety issues).
- Rescue medication.
- Non-treatment-related reasons, other than those already specified earlier. This includes situations like patients moving to another location for treatment unrelated reasons. Note that the “Treatment Policy” strategy might not be applicable if there are real lost-to-follow-up cases after doing all efforts to retrieve the data.

For deaths, the Treatment Policy cannot be applied, and missing data imputation will be used for the statistical analyses.

The “Treatment Policy” strategy implies that the efficacy observed assessment (including those collected after the occurrence of the intercurrent event) will be used regardless of the occurrence of an intercurrent event.

The “Composite” strategy will be applied to the following intercurrent events.

- Related death (or death with unknown reasons). It is expected that the rate of death at 52 weeks will be lower than that observed in the trial (<17%). A non-substantial but lower rate is expected in the experimental arm.
- “Real” lost to follow-up. These are cases where there is lost to follow-up after reasonable attempts to contact the patient have been made and all efforts to retrieve the data have failed.

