### **‘Survival Time’**

‘Survival Time’, i.e. time to death or time to reaching the criteria for respiratory insufficiency is the other key secondary endpoint. The criteria for respiratory insufficiency are defined as tracheostomy or initiation of non-invasive ventilation for more than 20 hours a day for more than 10 consecutive days, over 48 weeks or 72 weeks, respectively. Descriptive statistics (median and Q1/Q3 quartiles with 95% confidence intervals) and Kaplan-Meier curves will be provided. The difference between oral FAB122 and placebo will be assessed using restricted mean survival time (RMST) analysis for the time point week 48 (and another one for week 72 for the subgroup of 100 patients), adjusting for the stratification variables. The RMST analysis provides robust estimates even when the proportional hazard function is violated.

SAS PROC LIFETEST with option RMST will be used for this analysis.

In addition, a Cox regression model and a stratified log-rank test will also be applied as supportive analysis, including factors for treatment and stratification variables. Patients that complete the study and those that discontinue due to reasons other than death or due to reaching the criteria for respiratory insufficiency will be considered censored.

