### **Overall Survival**

Proportion of patients alive (survival rate) after 24, 48 and 72 weeks for full group and subgroup as available will be presented by treatment groups and overall. Kaplan-Meier plots will be presented, and treatment groups will be compared using a log-rank test.

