### **Staging of disease progression**

Data from staging of disease progression (King's scaling system, MiToS) after 12, 24, 60, 72 weeks as compared to baseline will be presented per visit by treatment group and overall, in summary tables using frequency and percentages. Frequency and percentages of patients showing a decline of  $\geq 1$  stage from baseline will be presented as well.

Kaplan-Meier curves will be created to present time to decline of  $\geq 1$  stage from baseline in both staging systems over 48 weeks or 72 weeks, respectively. A log-rank test will be used to determine the difference between study arms. Patients lost to follow-up will be censored. Days of maintaining the baseline stages will be presented per treatment arm and group/subgroup, including differences between treatment groups.

See section 9.1 for relevant derivations for King's scaling system and MiToS.

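### The week-24, 48 and 72 survival and event-free proportions (secondary efficacy items 10 and 11) count patients of unknown status as failures and should be Kaplan-Meier estimates

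*Protocol*

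**What the plan says.** **Items 10 and 11.** The Protocol (Synopsis, 3.2.2 and 11.3.4.3) lists item 10 as "Overall survival: Proportion of subjects alive (survival rate) after 24, 48 and 72" weeks and item 11 as "Proportion of subjects alive and no tracheostomy, or no initiation of non-invasive ventilation for more than 20 hours a day" (the ventilation must also last over 10 days in a row). For item 10, SAP 5.6.2 (Overall Survival) states: "Proportion of patients alive (survival rate) after 24, 48 and 72 weeks for full group and subgroup as available will be presented" by arm. The Progression free survival paragraph does the same for item 11. Both paragraphs add Kaplan-Meier plots and a log-rank test. Neither says how the proportion is estimated.

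**Rules that fill the gap.** SAP 5.1 and 5.2 both fix the denominator of a percentage as all patients in the relevant analysis population. SAP 5.6.2 (Other secondary endpoints) rules out imputation, intercurrent-event handling and sensitivity analysis for this group. The output list in SAP 10.3 keeps the proportion tables (14.2.10.1, 14.2.11.1) apart from the Kaplan-Meier figures (14.2.10.2, 14.2.11.2).

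**Item 9 (staging).** SAP 5.6.2 plans Kaplan-Meier curves and a log-rank test for time to decline, with loss to follow-up censored. It then adds: "Days of maintaining the baseline stages will be presented per treatment arm and group/subgroup, including differences between treatment groups". No estimator is given for those days.

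**The concern.** A patient who leaves before week 24, 48 or 72 with unknown status is in the denominator but cannot be in the alive count. Following the general rules therefore scores that patient as dead or as having had an event. If loss is more frequent in one arm, the two tabulated rates separate with no treatment effect.

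Protocol 11.4 expects more treatment discontinuation on FAB122: about 7% v 3% for adverse events and 10% v 5% for lack of efficacy. If some of those patients also leave follow-up, the artefact runs against FAB122.

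Days on baseline stage has the same weakness if computed as a plain mean, because short follow-up would count as short time on stage.

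Survival is the first secondary objective, and by-arm rates are easily quoted from a table. The risk is a table that contradicts the curve beside it.

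**Working it through.** **The plan's own figure.** Items 9 to 11 have none. The only sizing figure is for the primary endpoint: difference 3.0, SD 7.5, 2:1, two-sided 5%, 90% power.
- Placebo n = (1 + 1/2) x (1.960 + 1.282)^2 x 7.5^2 / 3.0^2 = 98.5, rounded up to 99, so 297 in total against 300 stated.
- Power at 200:100 is 90.4%.

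The figure reproduces, but it does not bear on these endpoints.

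**Inputs for the check**
- Treatment discontinuation for adverse events plus lack of efficacy (Protocol 11.4): 7 + 10 = 17% on FAB122, 3 + 5 = 8% on placebo.
- Deaths: below 17% at 52 weeks (SAP 5.2). At a constant hazard, 17% gives week-48 survival of 0.83^(48/52) = 84.2%. I assume 85% in both arms.
- Loss with unknown status: not in the documents, so a range is shown. The 6%/3% and 10%/5% pairs are assumptions; 17%/8% treats every such discontinuer as lost.

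**Crude proportion at week 48, no true effect.** With survival S and independent loss p, the tabulated proportion is S x (1 - p). The gap is -S x (p for FAB122 minus p for placebo).

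| Lost, FAB122 v placebo | Calculation | Gap (points) |
|---|---|---|
| 0% v 0% | 0.85 x 0 | 0 |
| 6% v 3% | -0.85 x 0.03 | -2.55 |
| 10% v 5% | -0.85 x 0.05 | -4.25 |
| 17% v 8% | -0.85 x 0.09 | -7.65 |

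**Simulation check.** This used 4,000 null trials of 200:100, 17% mortality at week 48, exponential deaths and uniform drop-out times. A share f of discontinuers (17% v 8%) is lost.

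| f | Crude gap (points) | Kaplan-Meier gap (points) | Log-rank rejections |
|---|---|---|---|
| 0 | -0.1 | -0.1 | 4.9% |
| 0.25 | -1.9 | 0.0 | 5.2% |
| 0.5 | -3.7 | 0.0 | 4.4% |
| 1 | -7.5 | -0.1 | 4.3% |

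The table is distorted; the planned curve and test are not.

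**Days on baseline stage.** Assume a median of 30 weeks (210 days) on stage and no effect. With hazard h = ln 2 / 210 and loss hazard c, mean observed days to day 336 = (1 - exp(-(h + c) x 336)) / (h + c).
- No loss: 203 days in both arms.
- 10% v 5% lost: 195 v 199.
- 17% v 8% lost: 188 v 196.

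In the simulation with 50% progressing by week 48 and f = 1, the plain mean differs by -9.6 days and the restricted mean by 0.1.

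**Item 11 wording.** The key secondary survival endpoint (Protocol 3.2.2; SAP 5.6.2, Survival Time) treats death, tracheostomy or qualifying ventilation as the event. Its complement is alive *and* no tracheostomy *and* no such ventilation. Item 11 puts *or* before the ventilation condition. Read literally, a patient who died without near-continuous ventilation meets that last limb and counts as event-free.

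**The case against.** The strongest reply is that censoring is already handled where the arms are compared. Kaplan-Meier curves and log-rank tests are planned for items 9, 10 and 11, and loss to follow-up is censored for staging. The key survival endpoint is assessed by restricted mean survival time with a stated censoring rule. All of that stands. A reader might infer that items 9 to 11 ignore censoring, or that no valid by-arm survival summary will exist; the documents support neither.

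The 17% and 8% are treatment stops, not lost patients. Protocol 4, 6.5 and 11.3.3 keep those patients in follow-up, Protocol 11.4 expects very little missing data for the primary endpoint, and the SAP takes death dates from a survival follow-up form. This stands too and makes -7.7 a ceiling. It does not remove the point: SAP 5.2 provides for real loss to follow-up, and Protocol 6.5 and 8.1.2 take patients out of the study at respiratory insufficiency. The SAP does not say whether the form covers their later deaths.

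The crude reading is inferred, since no estimator is named. It is nevertheless what the denominator rule yields, and the separate output tables do not correct it. The direction also depends on that reading: counting lost patients as alive would overstate survival by about 1.3 points on FAB122 and 0.6 on placebo at 17% v 8% lost, a small gap the other way.

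Two further inferences fail.
- The *or* in item 11 cannot add to a drop-out deficit, because it counts more patients as event-free.
- The SAP promises, for survival time, "Descriptive statistics (median and Q1/Q3 quartiles with 95% confidence intervals) and Kaplan-Meier curves will be provided". Deaths of 17% at 52 weeks imply 1 - 0.83^(72/52) = 22.7% at week 72, so one might conclude that the first quartile is never reached. That figure is deaths only. The endpoint also counts tracheostomy and ventilation, for which no rate is given, and 2.3 more points would reach 25%.

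**Conclusion.** The point holds for the tabulated proportions of items 10 and 11 and, if a plain mean is used, for days on baseline stage. With no true effect, the week-48 proportion gap is 0 with complete vital status, about -2.5 to -4.2 points at the assumed intermediate losses, and at most about -7.7. This rests on 85% survival in both arms, loss independent of death, and lost patients counted as not alive. The actual loss rate is unknown.

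The *or* in item 11 is a separate definition fault, repeated in both documents.

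Severity is minor. The endpoints lie outside the testing hierarchy and the SAP treats them as exploratory. No test on the proportions of items 10 and 11 is planned, and no confirmatory conclusion changes.

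**What to change.** 1. **SAP 5.6.2, Overall Survival and Progression free survival:** replace the crude proportions with Kaplan-Meier estimates at weeks 24, 48 and 72 (week 72 for the extended cohort), with 95% confidence intervals by arm and for the difference.
2. **SAP 5.6.2, Staging of disease progression:** define days on baseline stage as the restricted mean time to week 48, and to week 72 for the extended cohort, from the curve already planned.
3. **Item 11, as a separate correction:** in Protocol Synopsis, 3.2.2 and 11.3.4.3, and SAP 4.3 and 5.6.2 (Progression free survival), require alive *and* no tracheostomy *and* no initiation of the qualifying ventilation.

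Items 1 and 2 need SAP text and table shells only, since the curves are already planned. Item 3 also touches three Protocol sections. No new data, patients or power are needed. Kaplan-Meier and restricted means remove the artefact only where loss is unrelated to prognosis, so the SAP should also say how vital status is obtained after a patient leaves for respiratory insufficiency.
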